6 STUDY PROCEDURES/EVALUATIONS

6.1 Study Procedures

Recruitment

Within Limpopo Province, we will have two study sites, one in Vhembe and one in Capricorn district and these sites will recruit participants from a total 12 hospitals. In Tshwane (across both North West and Gauteng provinces) we will have one site in Soshanguve, and this will recruit participants from 33 clinics and two district hospitals. Within each site and clinic/hospital, we will seek to enroll all consecutive patients meeting the following inclusion criteria: (a) diagnosed with pulmonary TB at one of the study health facilities (including microbiological and/or chest x-ray diagnosis); (b) plan to pursue treatment within the study district; (c) willingness to provide informed consent and comply with study procedures. We will also include those patients who are recently deceased from the hospital register. Eligible participants will be identified by weekly review of the presumptive TB and TB treatment registers in each location, also in close collaboration with healthcare staff in each study health facility. We will approach all potentially eligible participants for informed consent at their treatment location within two weeks of diagnosis, making phone calls as necessary to contact participants who have been lost to follow-up between diagnosis and treatment initiation. For patients who are recently deceased, the next of kin will be contacted and asked if they can consent for the patient's information to be included in the study. Next of kin will also be asked to provide temporary consent for index patients who are too ill to consent at the time of enrollment. (These patients will be reapproached for consent once they have recovered to the extent of being able to complete the consent process.) After providing informed consent, participants will be randomized via a computer-generated algorithm to either routine or novel (holiday or off-peak) household contact investigation. Of note, participants who after consent and randomization, decline to accept household contact investigation - or who cannot be located at home at the time of home visit, will be included in the primary analysis as not resulting in a secondary case detected. Recruitment will be continued until 2400 participants are enrolled in each arm (expected to be completed within 28 months). For the bioethics sub-study, eligible participants will include all individuals who were enrolled in the parent study and completed follow-up for the primary outcome (including those who declined or were ineligible to participate in household contact investigation). For this sub-study, we will enroll consecutive eligible participants in each district until our desired sample size (~64 index cases and ~64 evaluable household contacts from each district) has been attained.

Data Collection: Contact tracing and interviews

Upon enrollment, we will conduct a detailed interview of all index cases, based on our current case report forms used in Limpopo. These interviews will include demographic, socio-economic and clinical characteristics, detailed data on mobility and migration, the preceding diagnostic cascade and symptom history, and extensive assessment of costs (including catastrophic health expenditures). Experience suggests that we can collect these data in 30 minutes. For patients

who are deceased or too ill to participate, the next of kin will complete the interview to the best of their ability. We will also collect a sputum sample from each living index case which will be sent for liquid MGIT culture in order to perform whole genome sequencing. After completing the interview, for cases assigned routine or off-peak contact investigation, an appointment time in the next two weeks will be arranged for the household visit. Cases allocated to holiday-time investigation will be asked for contact information and will be called within two weeks of the holiday to remind them of the study and set an appointment time for the household visit.

Study teams (2 in Limpopo and 2 in Soshanguve) consisting of a nurse and a research assistant trained in HIV counselling and testing will visit the household of each consenting index case (or legal guardian, in the case of minors). At the household, teams will recruit all available household members of all ages. For each enrolled participant, the team will conduct a similar interview to the index case on demographic, socio-economic, mobility/migration, health seeking behavior and clinical characteristics. Specifically, mobility questions will focus on spatial and temporal movement patterns over the previous year and will include: number and duration of trips away from primary residence, total duration of time away, destination and purpose of trips, longest distance travelled, longest trip duration, length of time living at primary residence and total number of lifetime moves. Each participant will be screened for TB as described above. Results on Xpert testing will be monitored by study staff using the electronic NICD laboratory system (tier.net), and participants will be notified either by phone or in person at a household visit if they have tested positive for TB and referred to the nearest public-sector clinic for treatment.

Empirical Assessment of Costs

We will conduct an empirical costing and associated cost-effectiveness analysis of the four contact investigation strategies from the societal perspective. Costs will be measured prospectively from study data and will comprehensively include those related to both health systems and patients. Health systems costs will be captured using an "ingredients" through a combination of budgetary review, key informant interviews (e.g., administrative staff), direct observation (e.g., time-motion studies of patients and study staff), and prospective logbooks kept by study staff and other relevant personnel (e.g., clinic nurses) Patient-level costs will be measured through patient interview, using the WHO Handbook on Tuberculosis Cost Surveys as a guide. We will also include other costs incurred by society, including additional costs to the national disability grant system (for which most TB patients are eligible), costs to the community "safety net" associated with having to perform contact investigation outside of regular business hours (e.g., any security concerns, childcare and other expenses for healthcare staff), and costs to caregivers to help patients complete the process of initiating TB treatment (for contacts who test positive). Costs from this "ingredients" approach will be compared (as a check) to a "topdown" approach in which we estimate large cost items (e.g., annual staff salaries) and divide those costs by the number of new TB cases identified and starting treatment under each strategy. We will also perform additional calculations for budget impact analysis, including estimating the size of the eligible population, the current number receiving contact investigation and the expected number receiving contact investigation after introducing novel implementation strategies, and any changes expected in TB-related costs following the introduction of this intervention.

Bioethics sub-study

Quantitative surveys

After obtaining written informed consent, trained data collectors will meet with participants either at their homes or in study clinics according to participant preference. Surveys will be conducted in the participant's choice of English or the local language in each district, and answers will be entered directly into an electronic database by study staff using mobile tablets. The interview will be pilot tested by study staff and designed to last a maximum of 30 minutes. Surveys will include participants' level of agreement with importance of household contact investigation; willingness to participate in household contact investigation; preferences for TB/HIV status disclosure; if (and to what extent) HIV testing contributes to the misconception that all people with TB have HIV; and whether HIV testing affects willingness to participate in household contact investigation. Question formats will include Likert scales, discrete choice experiments, best-worse scales, contingent valuation, and validated multi-item instruments (e.g., van Rie stigma scale²⁵). All data will be securely transmitted into a password protected REDCap database. The study data manager will routinely check all uploaded records daily for completeness, will run in- depth queries on a weekly basis, and ensure that all queries are resolved.

Qualitative interviews/focus group discussions

Each semi-structured, in-depth interview will be approximately one hour in length and will cover the following domains: TB/HIV disclosure preference, perceived stigma/blame, importance of household contact investigation, willingness to participate in household contact investigation, family invasiveness, community stigma/blame, duty to others health, and beliefs about TB/HIV confection. Six focus groups of ten participants each will be conducted in a private room at a central hospital in each district. Focus group discussions will last approximately two hours and will feature discussions on community-level perceptions and norms regarding the ethics of household contact investigation. No personal identifiers will be collected or used during the discussion. All in depth interviews and focus group discussions will be audio recorded, transcribed, translated as needed, and coded using Atlas.ti or NVivo. Thematic content analysis will be conducted to explore and document themes relating to participants' experiences, attitudes, and preferences in each domain.

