- 6. Sustainability of each novel strategy by reporting the primary outcome and fidelity measures according to six-month time period over the course of the study.
- Incremental cost-effectiveness ratio for each novel strategy. defined as (cost of contact tracing strategy 2 – cost of strategy 1)/(effectiveness of strategy 2 – effectiveness of strategy 1), where effectiveness is modeled as the number of disability-adjusted life years (DALYs) averted by the intervention. The primary cost-effectiveness measures will be the incremental cost per DALY averted using novel strategies (holiday and off-hours contact tracing) compared to routine contact tracing in each setting separately.
- 8. Experiences of inconvenience, attitudes toward confidentiality, motivation to participate, and preferences for disclosure, assessed through both thematic analysis of in-depth interviews and focus group discussions and quantitative analysis of discrete choice experiments and best-worst scaling.

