11.2 Sample Size Considerations

We estimate our sample size based on the assumption that 3% of household contacts will have tuberculosis (half the 6% prevalence seen in a previous study led by [name]),⁶⁴ and that an average of two contacts per case will be screened in the routine arm (based on our ongoing trial in Limpopo). Thus, in the routine arm, we anticipate a mean of 0.06 secondary cases per index case. Given the additional complexity of holiday-time or off-peak screening, we power our analysis under the *a priori* belief that such interventions will not be reasonably implemented unless they result in a yield that is twice that under routine contact investigation. Assuming an average of two to five contacts per household and a high (0.68) between-household coefficient of variation of the outcome as found in ⁶⁴, a comparison of n=1600 households (index cases) in the routine arm and 800 households (index cases) in the novel arm would have more than 99% power to detect this difference. If only half of the expected index cases are enrolled, the minimum power (two contacts per household) would be 84%. A maximally conservative estimate of sample size – assuming complete clustering of these cases at the household level, two contacts per household, and only 50% as many household cases.

We have selected our sample size to give more than 90% power to detect this most conservative difference. The table below provides estimates of our power to detect a statistically significant difference in the primary outcome.

Table. Power calculations. The power to detect each difference is given in italics; the primary comparison is between finding 0.06 secondary cases per index case in the routine arm and 0.12 in the novel screening arm.

		Mean number of secondary cases per index case, novel approach										
		0.08	0.1	0.12	0.18	0.24						
un er of dary per per case case ine	0.02	>0.99	>0.99	>0.99	>0.99	>0.99						
	0.04	0.99	>0.99	>0.99	>0.99	>0.99						
Me numk secor secor case: index , rou , rou	0.06	0.54	0.97	>0.99 (primary)	>0.99	>0.99						
	0.08	-	0.44	0.93	>0.99	>0.99						

Randomization

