- 7. Cost-effectiveness ratio for each novel strategy. Outcome measures will be derived by combining study data on patient characteristics (e.g., demographics, HIV status) and intervention effectiveness with literature estimates on key parameter values (e.g., disability weights,68 sensitivity of Xpert Ultra,69 and notified data on treatment outcomes¹) to construct a Markov model of a population of individuals who are eligible for TB screening under each strategy. In performing this evaluation, we will follow standard guidance for economic evaluation, including inflation using South Africa's GDP deflator, conversion to a common currency (US dollars) and year, discounting of all future costs and effectiveness, and measurement of costs as economic (opportunity) costs.^{70,71} We will conduct one-way sensitivity analyses of all model parameters and multiway sensitivity analyses of those parameters found to be most influential, in order to provide insight into the major drivers of cost-effectiveness and the settings in which each contact tracing strategy is likely to be preferred. We will also perform a probabilistic sensitivity analysis (using beta distributions for parameters with defined upper and lower bounds and gamma distributions for parameters defined from zero to infinity) to generate 95% uncertainty ranges around all estimates. We will construct cost-effectiveness acceptability curves, using as a reference South Africa's per-capita gross national income of \$5,430 as a willingness to pay per DALY averted⁷² but also considering revealed thresholds for potentially competing interventions (e.g., the estimated cost-effectiveness of treatments for MDR-TB for which the government of South Africa has revealed a willingness to pay).

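### As written, the societal cost-effectiveness analysis counts disability-grant transfers as a cost, which conflicts with the plan's own commitment to opportunity costs

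*Combined protocol and SAP*

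**What the plan says.** Under Empirical Assessment of Costs, section 6.1 announces a "cost-effectiveness analysis of the four contact investigation strategies from the societal perspective". After the health-system and patient costs it lists further costs that society bears, among them "additional costs to the national disability grant system (for which most TB patients are eligible"). The same list goes on to community and caregiver costs. Budget impact comes afterwards, as a further set of calculations.

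Section 11.4, secondary outcome 7, describes how the evaluation will be analysed. It promises to follow standard guidance for economic evaluation, including "measurement of costs as economic (opportunity) costs". It sets South Africa's per-capita income of $5,430 as the reference willingness to pay per DALY averted.

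Section 11.1 gives the measure that these costs feed: "The primary cost-effectiveness measures will be the incremental cost per DALY averted using novel strategies", compared with routine tracing separately in each setting. Section 8.1.2 says the same.

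Neither 6.1 nor 11.4 says that the grant item means administration only, that it is netted against what the patient receives, or that it is used only for budget impact.

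**The concern.** Opportunity cost is the value of resources used up. A cash grant uses up none beyond the work of administering it: the state is poorer and the patient richer by the same amount. In a societal analysis the payment should therefore either stay out or appear on both sides and cancel. Section 6.1 enters it on the cost side and names no matching gain. DALYs averted, the effect measure, would not record the money as a benefit.

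The item sits in the numerator of the primary cost-effectiveness measure and is tied to finding cases. If detecting an additional contact with TB leads to a net additional grant, the strategy that finds more cases carries a cost that society does not bear. The novel strategies, which the trial expects to have the higher yield, would then look less cost-effective than they are.

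**Working it through.** **Step 1. The plan's own yield.** Section 11.2 makes the "assumption that 3% of household contacts will have tuberculosis" and supposes that "an average of two contacts per case will be screened in the routine arm". Routine yield = 0.03 × 2 = 0.06 secondary cases per index case, as the plan states. The target for the novel arm is twice that, 0.12. The difference is dY = 0.12 − 0.06 = 0.06 extra cases per index case, or 0.06 × 800 = 48 extra cases per novel arm of 800.

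**Step 2. How the grant enters the ICER.** Let dC be the other incremental cost per index case, s the share of extra cases that receive a grant, G the net additional grant per such case, and D the DALYs averted per extra case.

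- ICER without the grant = dC / (dY × D)
- ICER with the grant = (dC + dY × s × G) / (dY × D)
- Difference = s × G / D

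dY cancels, so the shift per DALY does not depend on yield.

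**Step 3. Size.** The documents give no number for s, G or D. On s they say only "for which most TB patients are eligible". Assumed ranges: s 0.6 to 1.0, G $250 to $1,000, D 1 to 10.

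| Case | s | G | D | s × G / D | Share of $5,430 |
|---|---|---|---|---|---|
| Lowest | 0.6 | $250 | 10 | $15 | 0.3% |
| Illustration | 0.8 | $500 | 3 | $133 | 2.5% |
| Highest | 1.0 | $1,000 | 1 | $1,000 | 18.4% |

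Crossing s = 0.6, 0.8, 1.0 with G = $250, $500, $1,000 and D = 1, 3, 5, 10 gives 36 combinations. In 29 of them the shift is below 5% of the reference. Of the seven above 5%, six need D = 1.

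**Step 4. Check that yield drops out.** Use the illustration and an assumed dC of $20 per index case.

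| dY | ICER without grant | ICER with grant | Difference |
|---|---|---|---|
| 0.02 | 20 / 0.06 = $333 | 28 / 0.06 = $467 | $133 |
| 0.06 | 20 / 0.18 = $111 | 44 / 0.18 = $244 | $133 |
| 0.12 | 20 / 0.36 = $56 | 68 / 0.36 = $189 | $133 |

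The grant money added per index case does grow with yield (0.06 × 0.8 × $500 = $24 at the planned difference), but DALYs averted grow in the same proportion.

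**The case against.** The best reply is that the text speaks of costs to the grant system and never of payments. Administration is a real resource cost and belongs in the analysis. On that reading, or if the state's outlay is netted against the patient's receipt, 6.1 and 11.4 are compatible. Patient costs are to be collected by interview with a WHO handbook as guide, and the documents do not show whether that nets off grant income. Section 6.1 is also largely a list of what to collect, the budget impact analysis needs grant outlays, and an analyst who applied 11.4 strictly would leave the transfer out.

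Part of this stands: it would be too strong to say that the two sections can never be followed together. But the remark on eligibility points to payouts, the item is placed among society's costs before budget impact is introduced, and no offset or limit is stated. Following 6.1 as written puts a transfer into the ICER. If administration was meant, the same sentence of clarification is needed. The planned one-way and probabilistic sensitivity analyses vary parameter values; no run without the grant is specified.

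A reader might also infer three stronger things that the documents do not support:

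- **That every extra case is charged.** Only most patients are said to be eligible and only additional costs count. A contact who would have been diagnosed later might have drawn a grant anyway.
- **That the bias must run against the novel strategies.** This needs a positive net G and a higher novel yield. If earlier detection shortens disability or averts later claims, G could be near zero or negative.
- **That the penalty grows with effectiveness.** It does so in total cost but not per DALY, as step 4 shows.

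**Conclusion.** Wrong as written, for a secondary outcome. On its natural reading, 6.1 treats a transfer as a societal resource cost and conflicts with the costing principle in 11.4. The conflict can be seen from the plan's text alone. The direction and size of its effect cannot.

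If G is positive, each novel-versus-routine ICER is raised by s × G / D, whatever the yield. Under the assumed ranges this is about $15 to $1,000 per DALY averted, or 0.3% to 18% of the $5,430 reference. The low end is more likely: the top figure needs an additional $1,000 grant for every extra case with only one DALY averted, and grants that would have been paid anyway reduce G. Nothing here shows that a cost-effectiveness conclusion would change. The primary endpoint, its test and the power are unaffected.

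**What to change.** In 6.1 (Empirical Assessment of Costs) and 11.4 (secondary outcome 7), state that:

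1. Disability-grant payments are excluded from the societal base-case ICER, or are entered as a cost to the state with an equal gain to the patient. If they are excluded, grant income should not be deducted from patient costs either, or the error would run the other way.
2. Only the cost of administering any additional grants is kept as a societal cost.
3. Payments are reported in the budget impact analysis, or in a scenario labelled as the government payer's view.

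The cost is a few sentences, plus a source or a stated assumption for administration cost, because 6.1 names no source for it. The change should be made before cost-effectiveness results are seen, so that the choice is not made with the ICER in view.

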6.2 Laboratory Evaluations

6.2.1 Laboratory Evaluations/Assays

Liquid MGIT culture

Liquid MGIT culture is a mycobacterial growth assay that detects the presence of *Mycobacterium tuberculosis* directly from sputum. Xpert MTB/RIF assays will be carried out on sputum samples collected from participants. This assay will not be conducted under research conditions, but as part of routine South African standard of care, by the National Institute For Communicable Diseases (NICD). Sputum samples collected from

participants will be couriered by team couriers to NICD central laboratory for MGIT testing (see 6.2.3.2).

6.2.2 Special Assays or Procedures

Whole Genome Sequencing (WGS)

During the period of enrollment, we will work with the National Health Laboratory Services to perform culture and whole genome sequencing on all positive sputa. Bacterial isolates from standard culture will have total DNA extracted by staff at the NICD laboratory. WGS will be performed on the Illumina NextSeq platform. Nextera XT kit will be used to prepare libraries. Paired-end sequencing will be done with readlengths of 250 bp at >50x coverage. Alignment to a reference strain (H37Rv), variant filtering, and variant comparison will flow through a pipeline of five open-source tools (FastQC, BWA, Samtools, Freebayes, and Bedtools) following criteria commonly used in genomic analyses.

6.2.3 Specimen Collection, Preparation, Handling and Shipping

6.2.3.1 Instructions for Specimen Preparation, Handling, and Storage

Sputum collection is a routine clinical procedure that does not place the participant at any risk, and will be conducted by study staff only at household visits—the remainder of sputum collection for the study will be conducted by local clinic staff according to the standard of care. The participant will be instructed to go outside to provide the sputum sample. They should take several deep breaths, and hold each for 5 seconds, then cough such that sputum, if any, comes into their mouth. The participant then spits the sputum into the sputum collection jar and seals the lid on top, before handing to the study staff who then labels the specimen with participant details according to South African Department of Health standard procedures and places it inside of a sealed plastic bag then into a cooler until it is handed off to the NICD courier for transport to the NICD laboratory. At the laboratory, the sputum is processed immediately and tested by the Xpert MTB/RIF assay. No specimen is retained by the laboratory after testing

